7.1. Inclusion Criteria

1. Written informed consent obtained from subject or legal representative
2. ≥ 18 years of age
3. Diagnosis of NYHA Class III Heart Failure *Note: Subjects who are on continuous inotropic therapy should be considered in Stage D refractory heart failure and are not eligible for enrollment in the study.*
4. At least 1 HF hospitalization within 12 months of Baseline visit
5. Subjects with reduced LVEF heart failure should be receiving a beta blocker for 3 months and an ACE-I or ARB for one month unless in the Investigator's opinion, the subject is intolerant to beta blockers, ACE-I or ARB.
6. Subjects with a BMI ≤ 35 . Subjects with BMI >35 will require their chest circumference to be measured at the axillary level, if > 65 inches the patient will not be eligible for the study.
7. Subjects with pulmonary artery branch diameter ≥ 7 mm - (implant target artery - assessed during the RHC)
8. Subjects willing and able to comply with the follow-up requirements of the study

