8.6. Criteria for Withdrawal

Subjects may be withdrawn from the study for any of the following reasons:

1. Subject withdraws his/her consent
2. Investigator determines that other treatment is warranted to protect the health and safety of the subject

This confidential document is the property of Abbott and shall not be reproduced, distributed, disclosed or used without the express written consent of Abbott

Clinical Investigation Plan

3. Investigator determines that the subject is noncompliant with study related procedures
4. Subject is lost to follow-up: site must document attempts made to contact the subject for an early discontinuation visit (e.g., 2 – 3 phone calls, followed by 1 certified letter, documentation of repetitive missed study visits, etc.)

The Investigator will notify the Sponsor and document on the appropriate case report form (CRF) the reason/circumstances for early discontinuation. All subjects who withdraw from the study should have the following study exit procedures performed if possible:

- Updated medical and surgical history
- Assessment of AEs that occurred since the last visit
- Abbreviated physical examination (only significant changes since Enrollment) including vital signs (temperature, heart rate, respiratory rate, blood pressure), and weight
- Assessment of NYHA functional class
- Kansas City Cardiomyopathy Questionnaire(KCCQ-12)
- Brief Illness Perception Questionnaire
- Cardiac Health Security Survey
- Heart failure Medication Review
- PA pressures may be obtained at the Investigator's discretion

All reasonable efforts should be made to retain subjects in the clinical trial until its completion. If a patient moves from the geographic area of their investigator, St. Jude Medical will attempt to place the patient with another investigator.

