11.4. Procedures for Reporting Adverse Events (AEs)

It is the responsibility of the Investigator or Sub-Investigator(s) to perform periodic assessments of all AEs as well as identifying SAEs. Safety surveillance and reporting starts as soon as the patient is enrolled in the clinical investigation. Safety surveillance and reporting will continue until the last follow-up visit has been performed, the subject is deceased, the subject concludes participation in the clinical investigation or the subject withdraws from the clinical investigation.

AEs, ADEs, SAEs and SADEs that occur during the study should be treated by established standards of care that will protect the life and safety of the subjects.

Any AEs/ADEs are to be reported as soon as possible after knowledge of the event. SAEs/SADEs must be reported to the Sponsor no later than 3 calendar days from the day the site personnel became aware of the event or as per the investigative site's local requirements, if the requirement is more stringent than

This confidential document is the property of Abbott and shall not be reproduced, distributed, disclosed or used without the express written consent of Abbott

Clinical Investigation Plan

3 calendar days. If an SAE/SADE is not reported within the required time, it will be considered a protocol deviation. The date the site staff became aware of an event meeting the criteria of an SAE must be recorded in the source documentation.

The Sponsor will ensure that all applicable events and device deficiencies are reported to the relevant authorities as per regulations. The sites should notify the Sponsor of reportable AEs by creating and saving the applicable CRF within the electronic data capture (EDC) system. The description of the AE, date of the AE, treatment and resolution of the AE will be reported, as applicable per regulations, to the relevant authorities. Additional information may be requested, when required, by the Sponsor in order to support the reporting or adjudication of AEs. The Investigator must notify the IRB, if appropriate, in accordance with national and local laws and regulations, of the AEs reported to the Sponsor. Additional information with regard to an adverse event should be updated within the appropriate CRF.

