12.1. Populations for Analysis

Safety Population: The Safety Population consists of all subjects who received a Sensor implant or underwent the implant procedure but were never implanted, regardless of study completion status. All safety analyses will be performed on the Safety population.

Subjects who are found not to have an appropriately sized pulmonary artery branch and did not receive the Sensor implant will be considered ineligible for the study. However, these subjects will be followed for 30 days for safety and all safety related data for these subjects will be provided.

Effectiveness Population: The effectiveness population consists of all subjects who received a Sensor implant regardless of study completion status. All effectiveness analyses will be performed on the effectiveness population.

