12.3. Missing Data

Missing data will be tracked in the Electronic Data Capture system; queries will be generated and provided to the site. In addition, a St. Jude Medical representative, or designee will routinely perform monitoring visits at each site. During the monitoring visits, missing data queries will be addressed until resolution. Missing data that are not resolved will not be imputed unless specified in the sections below.

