12.7.1. Primary Effectiveness Endpoint

The primary time point for analyses is 12 months post-enrollment. The primary effectiveness endpoint will compare the annualized HF hospitalization rate parameter, γ , at 1 year versus the HF hospitalization rate in the year prior to enrollment using a two-sample, two-sided Poisson confidence interval. If the two-sided, upper 95% confidence interval for the PAS rate parameter is less than that in the year prior to enrollment, then the primary effectiveness endpoint will be met.

Mathematically stated, the primary effectiveness hypothesis is:

$$H_0: \gamma_{(12 \text{ month HF Hospitalization Rate})} \geq \gamma_{(\text{HF hospitalization rate in year prior to enrollment})}$$

$$H_a: \gamma_{(12 \text{ month HF Hospitalization Rate})} < \gamma_{(\text{HF hospitalization rate in year prior to enrollment})}$$

where $\gamma_{(12 \text{ month HF Hospitalization Rate})}$ = the HF hospitalization rate parameter at 1 year in the PAS and $\gamma_{(\text{HF hospitalization rate in year prior to enrollment})}$ = the HF hospitalization rate in the year prior to enrollment.

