APPENDIX L: Reporting of Interim Analyses

Updates from the PAS will be submitted to FDA as a PMA supplement every 6 months for the first two years of the study (annually thereafter). This information will include the following information:

Study enrollment and follow-up status

This confidential document is the property of Abbott and shall not be reproduced, distributed, disclosed or used without the express written consent of Abbott

Clinical Investigation Plan

Demographic information

	Premarket Study	PAS Aggregate	PAS Male	PAS Female
Average Age (years)	XX.X ± XX.X	XX.X ± XX.X	XX.X ± XX.X	XX.X ± XX.X
Male	XX.X%	XX.X%	XX.X%	XX.X%
Caucasian	XX.X%	XX.X%	XX.X%	XX.X%
Average BMI	XX.X ± XX.X	XX.X ± XX.X	XX.X ± XX.X	XX.X ± XX.X
Average LVEF	XX.X ± XX.X%	XX.X ± XX.X%	XX.X ± XX.X%	XX.X ± XX.X%
LVEF < 40%	XX.X%	XX.X%	XX.X%	XX.X%
Ischemic Cardiomyopathy	XX.X%	XX.X%	XX.X%	XX.X%
Average PA Systolic (mmHg)	XX.X ± XX.X	XX.X ± XX.X	XX.X ± XX.X	XX.X ± XX.X
Average PA Diastolic (mmHg)	XX.X ± XX.X	XX.X ± XX.X	XX.X ± XX.X	XX.X ± XX.X
Average PA Mean (mmHg)	XX.X ± XX.X	XX.X ± XX.X	XX.X ± XX.X	XX.X ± XX.X
Average PA Wedge (mmHg)	XX.X ± XX.X	XX.X ± XX.X	XX.X ± XX.X	XX.X ± XX.X
Average Cardiac Output (L/min)	XX.X ± XX.X	XX.X ± XX.X	XX.X ± XX.X	XX.X ± XX.X
Average Cardiac Index (L/min/m ²)	XX.X ± XX.X	XX.X ± XX.X	XX.X ± XX.X	XX.X ± XX.X

Safety

	6 Months N=XXXX		12 Months N=XXXX		18 Months N=XXXX		24 Months N=XXXX	
	N	Percent	N	Percent	N	Percent	N	Percent
DSRCs	XXX	XX.X%	XXX	XX.X%	XXX	XX.X%	XXX	XX.X%
Pressure Sensor Failures	XXX	XX.X%	XXX	XX.X%	XXX	XX.X%	XXX	XX.X%

Heart Failure Hospitalizations

	6 Months N=XXXX	12 Months N=XXXX	18 Months N=XXXX	24 Months N=XXXX
HF Hospitalizations	XXX	XXX	XXX	XXX
HF Hospitalization Rate:				
Events/patient years	X.XX	X.XX	X.XX	X.XX
Events/patient days	X.XX	X.XX	X.XX	X.XX
HF Hospitalization Proportion	XX.X%	XX.X%	XX.X%	XX.X%

Mortality

	6 Months N=XXXX		12 Months N=XXXX		18 Months N=XXXX		24 Months N=XXXX	
	Deaths	Percent	Deaths	Percent	Deaths	Percent	Deaths	Percent
All Cause Deaths	XXX	XX.X%	XXX	XX.X%	XXX	XX.X%	XXX	XX.X%
Cardiac Deaths	XXX	XX.X%	XXX	XX.X%	XXX	XX.X%	XXX	XX.X%
Non-Cardiac Deaths	XXX	XX.X%	XXX	XX.X%	XXX	XX.X%	XXX	XX.X%

This confidential document is the property of Abbott and shall not be reproduced, distributed, disclosed or used without the express written consent of Abbott

Clinical Investigation Plan

Serious Adverse Events

	6 Months N=XXXX		12 Months N=XXXX		18 Months N=XXXX		24 Months N=XXXX	

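### Withdrawal for noncompliance ends event collection in consenting, reachable subjects, so the 1-year HF hospitalization rate is likely to be understated if those subjects do worse

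*Combined protocol and SAP*

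**What the plan says.** - **Withdrawal.** The third criterion in section 8.6 applies when the "Investigator determines that the subject is noncompliant with study related procedures". It gives no definition or threshold. Withdrawal of consent and loss to follow-up are separate criteria, so this one reaches subjects who still consent and can be contacted.
- **End of collection.** Under section 11.4, surveillance and reporting continue until the last visit, death, or the point at which "the subject concludes participation in the clinical investigation or the subject withdraws from the clinical investigation". Hospitalizations over 24 hours and deaths are SAEs under section 11.2, so this stopping rule covers the effectiveness events as well as the safety events.
- **Retention.** Section 8.6 asks for exit procedures if possible, requires the reason for discontinuation on a CRF, and adds: "All reasonable efforts should be made to retain subjects in the clinical trial until its completion".
- **Analysis set and missing data.** Section 12.1: "The effectiveness population consists of all subjects who received a Sensor implant regardless of study completion status". Section 12.3: "Missing data that are not resolved will not be imputed unless specified in the sections below". No later section specifies imputation for the primary effectiveness endpoint.
- **Primary comparison.** Section 12.7.1 compares the annualized 1-year rate "versus the HF hospitalization rate in the year prior to enrollment using a two-sample, two-sided Poisson confidence interval". The interim shell in Appendix L expresses the rate as "Events/patient years".
- **Eligibility.** Section 7.1 requires "At least 1 HF hospitalization within 12 months of Baseline visit".

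**The concern.** The study is meant to confirm safety and effectiveness under commercial use, where imperfect compliance is part of what happens. The plan allows the investigator to end observation because of it. A withdrawn subject contributes events and person-time up to exit and nothing afterwards. If subjects leave for a reason linked to prognosis, the censoring is informative. Because the comparator is each subject's full prior year, the loss falls only on the follow-up side. No planned analysis examines it.

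At stake are the accuracy of the 1-year rate reported to FDA and in labeling, and the completeness of the 24-month safety endpoints. Section 12.6.1 bases those on a proportion with a Kaplan-Meier display, and neither can recover a complication or sensor failure that was never reported.

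**Working it through.** **1. The planning rates.** Section 13.4 gives an estimated Treatment rate of 0.52 and a CHAMPION Control rate of 0.75 per year. Exact one-sample Poisson power (reject when P(X ≤ c | 0.75n) ≤ 0.025) is 85.7% at n = 114 and 90.5% at n = 130, against the stated 85% and 90%. Inflation gives 130/(1 − 0.491) = 255.4, rounded up to 256. The plan's figures reproduce, so 0.52 and 0.75 are used below.

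**2. Size of the bias.** Let w be the fraction withdrawn for noncompliance, t the time of withdrawal in years, and r their yearly rate. All other subjects have rate 0.52.

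- Full-year rate = (1 − w) × 0.52 + w × r
- Observed rate = [(1 − w) × 0.52 + w × r × t] / [(1 − w) + w × t]

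The values of w and t are assumptions, because the documents give neither. With r = 0.75 and t = 0.25:

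| w | Observed | Full-year | Shortfall |
|---|---|---|---|
| 5% | (0.494 + 0.009375)/0.9625 = 0.523 | 0.494 + 0.0375 = 0.532 | 1.6% |
| 10% | (0.468 + 0.01875)/0.925 = 0.526 | 0.468 + 0.075 = 0.543 | 3.1% |
| 15% | (0.442 + 0.028125)/0.8875 = 0.530 | 0.442 + 0.1125 = 0.555 | 4.5% |

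Over a wider range (w = 5% to 30%, t = 3 or 6 months) the shortfall depends mainly on r:

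| r | Shortfall |
|---|---|
| 0.52 | zero |
| 0.75 | 1.1% to 7.9% |
| 1.04 | 2.3% to 15.6% |
| 1.5 | 4.2% to 24.5% |

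**3. Could it reverse the primary comparison?** If every subject meets the eligibility criterion, the prior-year rate is at least 1.0. Suppose 0.52 is observed and the unobserved rate after withdrawal is x. The full-year rate is then 0.52 + w(1 − t)(x − 0.52), which reaches 1.0 when x = 0.52 + 0.48/[w(1 − t)]. With t = 0.25:

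- w = 5%: x = 13.32 per patient-year
- w = 10%: x = 6.92
- w = 15%: x = 0.52 + 0.48/0.1125 = 4.79
- w = 30%: x = 2.65

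For the sub-study limit of 0.75 + 0.10 = 0.85, the required x is 1.99 to 13.7 over w = 5% to 30% and t = 3 or 6 months. These are point-estimate tipping points. A test based on a confidence limit would fail somewhat sooner.

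**4. Attrition.** Section 12.2 requires 619 and 663 subjects for the two safety endpoints and states 49.1% attrition. 1200 × (1 − 0.491) = 610.8, about 611. Exact power at 611 is 88.9% (0.80 against 0.85) and 86.6% (0.90 against 0.935), both under the stated 90%. The same sentence gives the fraction as 228/550, which is 41.5%. At that rate about 703 remain, enough for both endpoints. There is therefore no slack at the stated percentage, but there is some at the stated fraction.

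**The case against.** **Direction.** No section says that noncompliant subjects do worse. The criterion refers to study procedures, which include visits and three questionnaires as well as home readings, and missed questionnaires have no documented link to HF risk. This stands. The 0.52 and 0.75 rates support the direction only for subjects who stop supplying the pressures that guide their management, and even there it is an inference. A reader might infer that the rule necessarily lowers the rate in the device's favour. The documents support only that it is likely to do so if noncompliant subjects have more events.

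**Size.** The share withdrawn and the timing are unknown. A reader might infer a bias of 15% or more. That requires noncompliant rates around 1.04 or above together with large fractions withdrawn early, and nothing in the documents supports such values. Giving compliant subjects 0.75 would also be wrong, since that is the Control rate.

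**Effect on the conclusion.** A reader might infer that the primary result could be an artefact of this rule. Step 3 does not support that, given at least one prior-year hospitalization per subject.

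**Safeguards.** The rule is permissive, retention is encouraged, an exit assessment is requested, the reason is recorded, disposition is summarized, and compliance is itself analyzed. These limit the problem and make it visible. None of them collects an event after exit. Keeping all implanted subjects in the population retains only their time before withdrawal.

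**Attrition allowance.** The plan already inflates for attrition, and nothing shows that noncompliance withdrawals would exceed the allowance. That is fair. The point is only that these losses are avoidable.

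**Consent terms.** The consent template is not in the copy reviewed, so any terms there on data after withdrawal could not be checked.

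**Conclusion.** The concern holds in a limited form. The plan permits withdrawal for noncompliance, ends event reporting at that point, and has nothing that recovers or tests the effect of the missing events. The follow-up rate can therefore be informatively censored while the prior-year rate is complete.

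On the documents' own rates, with 5% to 15% assumed withdrawn at month 3, the understatement is about 1.6% to 4.5%. It is zero if noncompliant subjects have the same rate as the others and larger if they fare worse than 0.75. This is a bias in the reported estimate and is unlikely alone to change the primary conclusion. That judgement rests on an observed rate near 0.52, which is borrowed from the sub-study because section 12.2 states no rates for the main cohort, and on a prior-year rate of at least 1. The loss of 24-month safety information in implanted subjects does not depend on the direction of the bias.

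**What to change.** 1. In section 8.6, remove noncompliance as a reason to end study follow-up.
2. In sections 8.6 and 11.4, state that subjects who stop readings or miss procedures remain in follow-up for hospitalizations, deaths, device/system-related complications and sensor status to 24 months, by telephone or record review where visits are missed, unless they withdraw consent or are lost to follow-up.
3. Report withdrawals by reason, using the CRF entry that section 8.6 already requires.
4. In section 12.7.1, add a tipping-point analysis of the kind in step 3 for subjects already withdrawn under this criterion.

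The cost is a protocol amendment submitted to the IRBs of up to 150 sites, a check of the consent wording, and a small amount of site follow-up effort. Nothing changes in how subjects are treated or how the device is used. Version C is dated 19 February 2018, and Appendix A anticipated 738 of 1200 subjects enrolled by January 2017. If that timeline held, most subjects had passed 12 months when this version was issued. For them items 3 and 4 carry the 1-year analysis, while items 1 and 2 protect the remaining 12-month and 24-month follow-up.

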8.7. Deviations from CIP

A deviation is defined as an instance(s) of failure to follow, intentionally or unintentionally, the requirements of the CIP. The investigator should not deviate from the CIP.

In some cases, failure to comply with the CIP may be considered failure to protect the rights, safety and well-being of subjects; such non-compliance exposes subjects to unreasonable risks. Examples: failure to adhere to the inclusion/exclusion criteria, failure to report SAEs within given timeframe as per CIP, etc. Investigators should seek to minimize such risks by adhering to the CIP.

The PI must maintain accurate, complete, and current records, including documents showing the date of and reason for each deviation from the CIP. Relevant information for each deviation will be documented as soon as possible on the applicable CRF. The site will submit the CRF to the Sponsor.

The PI is required to adhere to local regulatory requirements for reporting deviations to the site IRB.

SAFETY ANALYSES

9.1. Primary Safety Endpoints

Primary safety endpoints will be evaluated at 2 years:

- 1) Freedom from device/system related complications

This confidential document is the property of Abbott and shall not be reproduced, distributed, disclosed or used without the express written consent of Abbott

Clinical Investigation Plan

2) Freedom from pressure sensor failure

9.1.1. Device / System-related Complication Criteria

A device / system-related complication is an adverse event that is, or is possibly, related to the system (wireless pressure sensor or external electronics) and has at least one of the following characteristics:

- is treated with invasive means (other than intramuscular medication or a right heart catheterization which is used for diagnostic purposes)
- results in the death of the subject
- results in the explant of the device

9.1.2. Sensor Failure Criteria

A Sensor failure occurs when no readings can be obtained from it after troubleshooting the system to rule out any problems with the external electronics.

EFFECTIVENESS ANALYSES

10.1. Primary Effectiveness Endpoint

- The primary effectiveness endpoint will compare the annualized HF hospitalization rate at 1 year in the study to the HF hospitalization rate in the year prior to enrollment.

10.2. Supplemental Analyses

10.2.1. Mortality

The mortality rate at 1 year in study will be analyzed.

10.2.2. HF Hospitalization or Death

The annualized HF hospitalization or death rate at 1 year in the study will be compared to the HF hospitalization rate in the year prior to enrollment.

10.2.3. Patient Compliance

Patient device usage over the course of the trial will be examined.

10.2.4. Training Evaluation

The effectiveness of the training program will be examined by community and academic hospitals.

10.2.5. Subgroup Analyses

The effectiveness analyses will be evaluated in each of the following subgroups: Women, Men, Reduced Ejection Fraction (< 40%), Preserved Ejection Fraction ($\geq 40\%$), Ischemic Etiology, Non-ischemic Etiology, With ICD/CRT-D, and Without ICD/CRT-D.

10.2.6. Quality of Life Evaluations

Patient reported outcomes will be evaluated using Quality of Life Questionnaires. The measures used will be the **Kansas City Cardiomyopathy Questionnaire-12 (KCCQ-12)**, the **Brief Illness Perception Questionnaire**, and the **Cardiac Health Security Survey**.

ADVERSE EVENTS

This confidential document is the property of Abbott and shall not be reproduced, distributed, disclosed or used without the express written consent of Abbott

Clinical Investigation Plan

11.1. Adverse Event (AE)

An AE is any untoward medical occurrence (e.g., noxious or pathological changes) in a subject compared with pre-existing conditions that may occur during any part of the clinical study. An AE is defined as being independent of assumption of any causality (e.g., primary or concomitant disease or study design). AEs should be evaluated by the Investigator and maintained in the research records at the site. AEs should be reported to the Sponsor on a CRF.

11.2. Serious Adverse Event (SAE)

For this study, an SAE is defined as any untoward medical occurrence that:

- results in death
- is immediately life-threatening – an event in which the subject was at risk of death at the time of the event
- requires admission and hospitalization (> 24 hours) or prolongation of existing hospitalization
- results in disability/incapacity
- results in a congenital anomaly/birth defect
- requires intervention to prevent one of the above

SAEs, as determined by the Investigator, must be reported to the Sponsor.

The cause of death of any subject after enrollment must be documented on the AE CRF and reported as an SAE. The information should include the date expired, cause of death, and what attempts were made to treat the condition.

If it is not certain that an event meets the above definition, contact the Project Manager.

